5.3.2. Secondary Endpoints

For the secondary endpoints, treatment groups will be compared based on each of the following:

1. Rate of achieving a plasma glucose concentration > 70 mg/dL (> 3.88 mmol/L) within 30 minutes from injection of study drug.
2. Rate of achieving an increase in plasma glucose concentration ≥ 20 mg/dL (≥ 1.11 mmol/L) within 30 minutes from injection of study drug.
3. Rates of positive symptomatic response, defined as relief of neuroglycopenic symptoms within 30 minutes from a decision to dose.
4. Rates of positive treatment response, defined as exhibiting either a positive plasma glucose response *or* a positive symptomatic response.
5. Time to a positive plasma glucose response from injection of study drug.
6. Time to administer study drug from a decision to dose.
7. Pharmacodynamic (PD) characteristics of mean plasma glucose concentration (0 to 90 minutes post-dose), maximum observed concentration (C_{max}), time to maximum observed concentration (t_{max}), area under the concentration versus time curve from time 0 to 90 minutes ($AUC_{(0-90)}$), and area under the concentration versus time curve from time 0 to 180 minutes ($AUC_{(0-180)}$).
8. Time to (a) initial relief and (b) complete resolution of autonomic and neuroglycopenic symptoms of hypoglycemia from a decision to dose.
9. Time to resolution of the overall feeling of hypoglycemia from a decision to dose.
10. Safety endpoints, including: adverse event (AE)/serious adverse event (SAE) rates, and changes in vital signs, laboratory variables, and physical exam/electrocardiogram (ECG) findings.

11. Tolerability endpoints, including: Draize scale scores for injection site erythema and edema as assessed by the investigator, and injection site discomfort and duration as assessed by subject questionnaire responses.

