5. Subcutaneous administration of the study drug will be made to the abdomen around the umbilicus as per [Section 9.3.3](#). Clock time of study drug administration will be recorded in the source documents. After study drug injection, the study product will be disposed in a location away from the subject in a manner that maintains the blind. After disposal, the blindfold and headphones will be removed from the subject.
6. Following study drug administration, plasma glucose will be measured every 5 ± 2 minutes through 90 minutes, and every 30 ± 2 minutes thereafter through 180 minutes post-dosing.

7. At 180 minutes post-dosing, the subject will resume insulin therapy and be given a meal as per the standard practice at each site. The subject can be discharged from the clinic if their plasma glucose is >100 mg/dL (> 5.55 mmol/L) and the subject is deemed medically stable.
8. After study drug administration and before 180 minutes post-dosing, if rising glucose levels are observed and if deemed medically necessary, insulin therapy or other medical intervention may be initiated by the Investigator.
 - a. Such intervention is not recommended to occur before 90 minutes post-dosing of study drug.
 - b. Plasma glucose data and assessments of neuroglycopenic symptoms will be censored after the time of intervention, per the statistical analysis plan.
 - c. These interventions (such as insulin, carbohydrates, or a meal) prior to 180 minutes post study drug administration should be captured in the source documents, and further glucose measurements may be performed at the discretion of the Investigator.

Hypoglycemia Symptom Assessments

Subjects will complete a questionnaire regarding severity of hypoglycemia symptoms ([Appendix 1](#)) at the following time points:

1. Just before the IV bolus push dose of insulin is given at the start of the hypoglycemia induction procedure (baseline),
2. Every time blood is drawn for evaluation of plasma glucose concentration during the induction procedure,
3. Just before study drug is administered,
4. Every 5 ± 2 minutes after glucagon is administered until 90 minutes post-dosing, and every 30 minutes (coinciding with plasma glucose measurements) between 90 and 180 minutes post study drug administration.

Local Tolerability and Adverse Events

Local tolerability and AEs will be assessed as follows:

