5.3.6.2 Secondary Endpoints

5.3.6.2.1 Pharmacodynamic (PD) Parameters

The PD endpoints will be derived from the individual glucose profiles. Pharmacodynamic characteristics, including:

- AUC_{0-90} and AUC_{0-180} : plasma glucose area under the concentration versus time curve for 90 and 180 mins from glucagon administration;
- C_{max} : Maximum concentration of glucose in plasma;
- T_{max} : time (in mins) when Glucose C_{max} is reached;

The following rules will be used for incomplete data:

- AUC: If there are missing data points before the last observed value, they will be extrapolated using the last two data points;
- AUC: If there are missing data points after the last observed value, they will not be imputed, and the AUC will be treated as not defined;
- If insulin starts after receiving glucagon, the glucose values post insulin start will be censored out and considered as missing. This is also considered a major protocol deviation.

Comparison between the treatments will be performed using a mixed model with treatment, period and treatment*period as fixed factors and subject as a random factor.

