6.6.2 Pharmacodynamics Analyses

All PD parameters will be presented descriptively.

A mixed model with treatment, period and treatment*period as fixed factors and subject as a random factor will be applied to compare the least square mean differences. Log transformation will be applied if skewness is observed. Unstructured covariance matrix will be used for the covariance matrix unless the model failed. In such case, structured covariance matrix will be selected based on the one given the smallest AIC (Akaike Information).

P-value for the difference test and 95% confidence for non-inferior test will be reported.

Additionally, mean glucose curve from 0 to 180 minutes post receiving glucagon will be presented graphically for each treatment. For this group of figures, the protocol defined time will be used. The mean glucose curve during hypoglycemia induction time will also be presented for each treatment. Since there is no protocol time for hypoglycemia induction stage, the mean glucose will be summarized for every 5 minutes based on the glucagon injection time.

This will be conducted based on the mITT population only.

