7 DATA HANDLING CONVENTIONS

7.1 Missing Data

Unless specified in any of the previous sections, no other missing data will be imputed.

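### Cmax and Tmax from profiles cut off at insulin start are analysed as fully observed, although they are only lower bounds when glucose was still rising

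*SAP*

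**What the plan says.** SAP 5.3.6.2.1 gives AUC two explicit windows. Cmax is only "Maximum concentration of glucose in plasma" and Tmax only "time (in mins) when Glucose C_{max} is reached". The endpoint list in Protocol 5.3.2 reads "mean plasma glucose concentration (0 to 90 minutes post-dose), maximum observed concentration", so its 0-90 minute window belongs to the mean concentration and not to the maximum.

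For a subject who starts insulin after glucagon, "the glucose values post insulin start will be censored out and considered as missing". The two rules for incomplete profiles are both labelled AUC. For points missing after the last observed value, "they will not be imputed, and the AUC will be treated as not defined". Nothing equivalent is given for Cmax or Tmax, and SAP 7.1 adds: "Unless specified in any of the previous sections, no other missing data will be imputed".

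Protocol 10.2.1.2 (Preparation and Administration of Study Drug, step 8) sets the trigger: "if rising glucose levels are observed and if deemed medically necessary, insulin therapy or other medical intervention may be initiated by the Investigator". It advises against intervening before 90 minutes and leaves the censoring to the SAP.

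For the comparison, SAP 6.6.2 says: "A mixed model with treatment, period and treatment*period as fixed factors and subject as a random factor will be applied". It restricts this work to the mITT population. SAP 5.3.6.2.1 also classes insulin after glucagon as a major deviation, which under SAP 5.1.3 removes the subject from the per-protocol set only.

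**The concern.** One interrupted profile is treated in two ways. Its AUC0-180 is withdrawn because the end of the curve is unknown. Its Cmax and Tmax, which depend on the same unknown part, are kept as if the whole curve had been seen.

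The cut is linked to the outcome. If glucose was still rising when insulin began, the true peak lies later and higher than any retained reading. The mixed model has no means of distinguishing such a value from a real peak. The investigator who decides on insulin knows the treatment (Protocol 9.2), so the share of profiles cut off may differ between drugs. Cmax and Tmax are named secondary endpoints, and SAP Appendix 1 plans a comparison table for each.

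**Working it through.** **No plan figure to reproduce.** The documents give no mean, SD, margin or power for Cmax or Tmax, and no expected frequency of early insulin. All sizes below rest on assumed profiles. Only the sampling times come from the protocol: every 5 minutes to 90, then 120, 150 and 180.

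**1. Direction.** Let p be the share of visits cut off and L the mean loss in a cut-off visit, for test (T) and reference (R):

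observed difference = true difference - p_T x L_T + p_R x L_R

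Each drug's own mean is pulled down. The difference shrinks if p_T x L_T exceeds p_R x L_R and grows if the reverse holds.

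**2. Size, first illustration.** Assumed curve: 48 + (C - 48) sin(pi/2 x min(t/T, 1)), then a fall of 0.25 mg/dL per minute after the peak. Mean peak C is 210 v 195 mg/dL and mean peak time T is 110 v 90 minutes. Between-subject SDs are 30 mg/dL and 15 minutes; within-subject SDs are 20 mg/dL and 15 minutes. Insulin starts at a random time from 90 to 120 minutes in a fraction f of visits still rising at 90.

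| Insulin given | f | Cmax difference | Tmax difference (min) |
|---|---|---|---|
| nobody (true) | 0 | 14.5 | 20.3 |
| same rule for both drugs | 5% | 14.2 | 19.6 |
| same rule for both drugs | 10% | 13.9 | 18.9 |
| same rule for both drugs | 20% | 13.3 | 17.6 |
| same rule for both drugs | 40% | 12.1 | 14.9 |
| higher, later-peaking drug only | 40% | 11.3 | 11.9 |
| lower, earlier-peaking drug only | 40% | 15.3 | 23.3 |

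The formula accounts for the same-rule 40% row. Cut-offs on the later-peaking drug alone remove 14.5 - 11.3 = 3.2 mg/dL and 20.3 - 11.9 = 8.4 minutes. Cut-offs on the other drug alone add 15.3 - 14.5 = 0.8 mg/dL and 23.3 - 20.3 = 3.0 minutes. Together: 14.5 - 3.2 + 0.8 = 12.1, and 20.3 - 8.4 + 3.0 = 14.9.

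In the later-peaking drug's cut-off visits Tmax was always 90 minutes, while mean insulin time was about 105. Cmax was about 9 mg/dL too low, or 13 with peak times of 120 v 90.

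**3. Size, second illustration.** Assumed curve: 50 + (C - 50)(t/T) exp(1 - t/T). Mean peak is 220 v 200 mg/dL (SD 30 between, 15 within). Test peaks 10 minutes later (SD 15 between, 10 within). Insulin starts at the first rising reading from 90 minutes above 200, 230 or 260 mg/dL. The true differences are about 20 mg/dL and 10 minutes.

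| Reference peak time | Tmax difference at 200/230/260 | Cmax difference at 200/230/260 |
|---|---|---|
| 80 min | 6.6 to 9.4 across thresholds | 19.4 to 19.8 across thresholds |
| 100 min | 2.0 / 5.8 / 9.2 | 18.0 / 18.8 / 19.6 |
| 120 min | -2.9 / 2.7 / 8.0 | 16.0 / 17.9 / 19.4 |

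At a 100-minute peak these thresholds mean insulin in 65/34/10% v 37/14/3% of subjects. The one sign change needs insulin in about 71% v 48%.

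**4. Candidate remedies on the second model.**
- *A 0-90 minute window:* the Tmax difference becomes 6.1, 2.0 and 0.3 minutes for peaks at 80, 100 and 120, and the Cmax difference 19.2, 17.7 and 16.0 mg/dL. At the 120-minute peak, 96-99% of subjects have Tmax of 90.
- *Right-censored Cmax in a normal model:* the difference rises to as much as 50 mg/dL against a true 20, because censoring depends on glucose itself.
- *Right-censored Tmax in a normal model:* 10.3 to 12.4 minutes over the nine settings, against -2.8 to 9.5 in a rerun of the SAP rule.
- *Right-censored Tmax as a Kaplan-Meier mean restricted to 180 minutes* (events before censorings at ties; run as a check for this point): 11.1 to 15.3 minutes. This is nearer the truth than the SAP rule in the six settings with peaks at 100 or 120, and further away in the three at 80. A profile censored at 90 is passed on to 120 or later, although its sampled maximum might have been at 90.

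**The case against.** The SAP is not silent. Its censoring sentence covers all glucose values, other imputation is barred, and the endpoint is named as a maximum observed value over post-dose sampling to 180 minutes. A programmer would therefore take the largest retained reading over an implicit 0-180 window. That is a fair reading, and it is the problem: it enters a lower bound as an observation.

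Insulin need not mean an unreached peak. Step 8 speaks of rising glucose having been observed, and does not say that it is still rising when insulin starts. The Synopsis (Study Methods) also lets investigators restart insulin or bring the meal forward from 90 minutes for other reasons, including preventing rebound hypoglycemia. This stands, so the lower-bound argument applies only where the last reading before the intervention is the highest.

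Early insulin may be rare. Calling it a major deviation suggests that high frequencies were not foreseen, and when it is rare the distortion is small. This stands as well.

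The consequence is limited. The Cmax and Tmax tables are titled non-inferiority, but neither endpoint has a margin, and no success rule uses the result. That rules out any claim about the trial's main conclusion.

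**Conclusion.** The point holds in limited form. Following the SAP as written puts lower bounds for Cmax and Tmax into the mITT mixed model as observed values whenever insulin cuts off a glucose curve that is still rising. Both are biased downward in those visits, and Tmax is affected most.

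The size depends on how often insulin starts early, which the documents do not give. On the first set of assumed profiles, with one rule for both drugs, the differences moved by 0.3 mg/dL and 0.7 minutes at 5% of still-rising visits, and by 2.4 mg/dL and 5.4 minutes at 40%.

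Four stronger readings are tempting and are not supported:
- *Tmax equals the insulin time.* It is the last reading before insulin, which after 90 minutes can be up to about 30 minutes earlier.
- *A real drug difference is necessarily masked.* The difference can also be exaggerated, depending on which drug is cut off more. The documents do not settle that.
- *The primary result is at risk.* It is read within 30 minutes of injection, and intervention is discouraged before 90.
- *A 0-90 minute window is the remedy.* It cuts off every late peak.

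**What to change.** In SAP 5.3.6.2.1 and 6.6.2:

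1. State that Cmax and Tmax are derived over 0-180 minutes after injection.
2. Flag every profile whose maximum is the last reading before an intervention, and report the number flagged by drug.
3. Analyse Tmax with flagged profiles right-censored at that reading, using the time-to-event approach already planned for the other timing endpoints. The Appendix 2 code has no censoring indicator, so one must be added. State how ties at the censoring time are handled, and give a censored regression alongside, because the Kaplan-Meier mean overshot in the check above.
4. Present Cmax with flagged values identified as lower bounds. Add a sensitivity analysis, for example adding a range of fixed increments to flagged values separately by drug. Do not rely on a right-censored Cmax model.
5. Do not make a 0-90 minute Cmax or Tmax the main comparison.

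Two related inconsistencies need reconciling. SAP 6.6.2 names the mITT population, while the Cmax and Tmax comparison tables in Appendix 1 name ITT. SAP 5.3.6.2.1 classes insulin after glucagon as a major deviation, while Protocol 10.2.1.2 permits it.

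The cost is SAP wording, one flag and a modest amount of extra programming on data already collected. Censoring of Tmax may remain partly informative, and a log-rank test stratified by treatment alone does not use the within-subject pairing.

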After 180 minutes posttreatment, subjects will resume insulin pump therapy, if applicable, and will be given a meal. Subject may be discharged after 180 minutes posttreatment if their plasma glucose is > 100 mg/dL (5.56 mmol/L) and if medically stable. At the Investigator’s discretion, subjects’ prescribed insulin regimen can be restarted, or the meal can be given sooner, but not earlier than 90 minutes post-glucagon treatment, to prevent hyperglycemia or rebound hypoglycemia.

After a wash-out period of 7 to 28 days, subjects will return to the CRC and the study procedures will be repeated with each subject crossed over to the other treatment. After study-related procedures are performed on each of the treatment days, subjects will be discharged. A Follow-Up Visit will be

XSGP-304 Clinical Protocol
G-Pen (glucagon injection)

	
conducted 2 to 7 days after administration of the final dose of study drug as a safety check.
 
Tolerability will be assessed by comparing AE reports between the G-Pen and GlucaGen Hypokit treatment groups. In addition, at the end of each treatment period the subjects will complete questionnaires to assess injection site discomfort, and the Investigator will use a modified Draize scale to evaluate the injection sites after each administration.

Data management and statistical analysis:	
Data will be entered into an electronic Case Report Form (eCRF) by the study site personnel. Data will be monitored at on-site visits by Xeris personnel or by a contract research organization (CRO) delegated by Xeris. A stand-alone Statistical Analysis Plan (SAP) will be written to detail all protocol specified analyses. The SAP will take precedence over the protocol. The primary endpoint will be analyzed using an exact test procedure based on the conditional distribution for a maximum clinically acceptable non-inferior margin of $\leq 5\%$.

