Initial IV bolus push dose will be calculated as 75% of the dose estimated to reduce plasma glucose from the subject's starting plasma glucose level (SG) to desired glucose level 54 mg/dL (3.0 mmol/L) based on the subject's self-reported glucose correction factor. This dose will be referred to as "first bolus (full bolus dose)" (BD1) subsequently:

$$\text{BD1 (mg/dL)} = [(\text{SG} - 54 \text{ mg/dL}) / \text{Correction factor}] \times 0.75.$$

- **Randomization.** Once the initial bolus dose of insulin has had time to take effect and the subject is observed to be in a controlled rate of glucose decline, the subject will be randomly assigned to one of the treatment sequences shown in Table 1.
- **Confirmation of Hypoglycemic Steady State.** Once the initial plasma glucose measurement < 54.0 mg/dL (< 3 mmol/L) is achieved, the IV insulin infusion will be returned to the rate established at the end of the baseline euglycemia steady state period. After 5 minutes, the IV insulin infusion will be stopped, and up to 3 confirmatory plasma glucose readings will be taken at subsequent 5-minute intervals to determine whether a hypoglycemic steady state has been reached.

A *hypoglycemic steady state* is defined as a confirmatory plasma glucose value ≥ 42 mg/dL (≥ 2.33 mmol/L) and < 54 mg/dL (< 3 mmol/L), and an 8-minute linearly extrapolated future plasma glucose value ≥ 42 mg/dL (≥ 2.33 mmol/L).

- **Decision to Dose.** Once the hypoglycemic steady state is confirmed, the Investigator will confirm that it is appropriate to administer study drug to the subject. The clock time of this "Decision to Dose" will be captured in the source documents. Decision to dose time is entered on the Induction CRF for each visit and will be used in the analysis.
- **Preparation and Administration of Study Drug.** Following a decision to dose, subjects were administered a subcutaneous injection around the umbilicus with either 1 mg GlucaGen Hypokit or 1 mg G-Pen.
- **Post-dose assessments.** Blood glucose levels will be monitored for up to 180 minutes post-dosing. Subjects will also complete a questionnaire about symptoms of hypoglycemia during the hypoglycemia induction phase and for up to 180 minutes after treatment with glucagon.

Plasma glucose levels and assessments of neuroglycopenic symptoms will be censored after the time of drug administration. This censoring is applicable only if the insulin is

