restarted prior to the 180 minutes timepoint as per the following language in the protocol:

“After study drug administration and before 180 minutes post-dosing, if rising glucose levels are observed and if deemed medically necessary, insulin therapy or other medical intervention may be initiated by the Investigator.

- a. Such intervention is not recommended to occur before 90 minutes post-dosing of study drug.
- b. Plasma glucose data and assessments of neuroglycopenic symptoms will be censored after the time of intervention, per the statistical analysis plan.
- c. These interventions (such as insulin, carbohydrates, or a meal) prior to 180 minutes post study drug administration should be captured in the source documents, and further glucose measurements may be performed at the discretion of the Investigator.”

The specific hypoglycemia induction procedures and justification, and rules for interruption and termination of dosing are specified in the protocol.

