5.1.3 Per-Protocol Population (PP)

The Per-Protocol (PP) population is defined as all randomized patients who during both study periods successfully receive a dose of both study drugs (G-Pen followed by GlucaGen Hypokit or GlucaGen Hypokit followed by G-Pen) and have no any major protocol deviations. The actual treatment received will be used for analysis.

Primary endpoint comparison and secondary efficacy analyses will be performed for ITT, mITT and PP populations.

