5.3.6.1 Primary Endpoint

Positive Plasma Glucose Response 1 (PGR1)

Positive Plasma Glucose Response 1 (PGR1) is defined as reaching a plasma glucose concentration ≥ 70 mg/dL (≥ 3.88 mmol/L) within 30 minutes of study drug injection (actual time). (The baseline plasma glucose is the blood glucose reading immediately before study drug dosing.)

Positive Plasma Glucose Response 2 (PGR2)

Positive Plasma Glucose Response 2 (PGR2) is defined as reaching an increase in plasma glucose concentration ≥ 20 mg/dL (≥ 1.11 mmol/L) within 30 minutes of study drug injection (actual time).

Positive Plasma Glucose Response (PGR)

For the primary endpoint, Positive Plasma Glucose Response (PGR) is defined as reaching Positive Plasma Glucose Response 1 (PGR1) **or** Positive Plasma Glucose Response 2 (PGR2).

For the primary endpoint, treatment groups will be compared for rates of achieving a positive plasma glucose response. The comparison will be performed using Intention to Treat (ITT), Modified Intent-to-Treat (mITT) and the Per-Protocol (PP) populations. Risk difference in rates of failing to achieve Positive Plasma Glucose Response (PGR) will be assessed for G-Pen versus GlucaGen Hypokit used as reference and the associated 95% CIs presented.

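### SAP 5.3.6.2.1 makes insulin that the protocol permits after the 30-minute endpoint a major deviation, which needlessly shrinks the Per-Protocol set

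*SAP*

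**What the plan says.** **The rule.** SAP 5.3.6.2.1 lists conventions for incomplete glucose profiles. For insulin started after glucagon, "the glucose values post insulin start will be censored out and considered as missing. This is also considered a major protocol deviation". The bullet has no time limit.

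**Its consequence.** Under SAP 5.1.3, PP subjects must have received both drugs and "have no any major protocol deviations". SAP 6.5 runs the non-inferiority analysis in ITT, mITT and PP, and names none of them as decisive.

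**What the protocol allows.**
- Synopsis, Study Methods: at the investigator's discretion the "prescribed insulin regimen can be restarted, or the meal can be given sooner, but not earlier than 90 minutes post-glucagon treatment".
- Section 10.2.1.2, Preparation and Administration of Study Drug, step 8: before 180 minutes, "if rising glucose levels are observed and if deemed medically necessary, insulin therapy or other medical intervention may be initiated by the Investigator". Step 8a advises against this before 90 minutes but does not forbid it. Step 8b gives the consequence: glucose and neuroglycopenic symptom data are censored from then on.
- Step 7 of the same section, for every subject: "At 180 minutes post-dosing, the subject will resume insulin therapy and be given a meal".

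SAP 4.1 reproduces step 8 and says of the censoring: "This censoring is applicable only if the insulin is" "restarted prior to the 180 minutes timepoint".

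**The concern.** The SAP labels as a major deviation something that its own section 4.1 reproduces as permitted care. Because PP requires both periods, one permitted restart removes two completed primary outcomes.

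Excluding subjects from PP makes sense when the conduct could have affected the outcome. Under SAP 5.3.6.1 the primary response must occur within 30 minutes of injection, so insulin at 90 to 180 minutes comes after the result is fixed. Dropping these subjects costs PP precision and gives nothing back for the primary question.

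The change is also undeclared. Protocol 13.3 defines PP by successful induction, hypoglycemic steady state and receipt of both drugs, with no clause on major deviations, and would keep these subjects. SAP section 2 undertakes to identify substantial differences from the protocol. Section 10 lists only the move from mixed models to time-to-event analysis for the timing parameters.

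**Working it through.** **Step 1. Which insulin is meant.** Taken literally, the bullet catches everyone, because all subjects resume insulin at 180 minutes. SAP 4.1 limits the linked censoring to restarts before 180 minutes, so that is the workable reading.

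**Step 2. Permission by time after injection.**

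| Insulin started | Protocol | Can it change the primary endpoint? |
|---|---|---|
| 0–30 min | Synopsis bars a regimen restart; step 8 advises against intervention but allows it if medically necessary | Yes |
| 30–90 min | As above: synopsis and body differ | No |
| 90–180 min | Permitted in both places | No |

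The conflict with the SAP is therefore unambiguous for 90–180 minutes. The irrelevance to the primary endpoint covers 30–180 minutes.

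**Step 3. Loss from PP.** The documents give no restart rate, so the plan has no figure to reproduce. Take the planned 111 evaluable subjects (Protocol 13.2) and *assume* a share r of visits with a restart, independent between visits. PP then keeps 111 × (1 − r)². The Appendix 2 code treats the arms as unpaired, so the upper limit is d + 1.96 × √[p₁(1−p₁)/n + p₂(1−p₂)/n]. For illustration, assume 2 G-Pen failures, no GlucaGen failures, and only successes lost:

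| r | PP n | Upper limit | Limit ≤ 5%? |
|---|---|---|---|
| 0 | 111 | 1.80% + 2.48% = 4.28% | yes |
| 2% | 107 | 4.44% | yes |
| 5% | 100 | 2.00% + 2.74% = 4.74% | yes |
| 10% | 90 | 2.22% + 3.05% = 5.27% | no |
| 20% | 71 | 6.67% | no |

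The 5% cap on the G-Pen failure rate tightens in the same way: 5/111 = 4.5%, but 5/90 = 5.6%.

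**Step 4. Single exclusions.** Losing one subject with a failure can move the PP result either way (assumed counts, G-Pen versus GlucaGen):
- 3 v 2 of 111 gives 4.80% (passes). Without one GlucaGen failure, 3 v 1 of 110 gives 5.34% (fails).
- 3 v 0 of 111 gives 5.72% (fails). Without one G-Pen failure, 2 v 0 of 110 gives 4.31% (passes).

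**Step 5. Average effect.** Simulation of 111 subjects with equal true failure rates and restarts independent of outcome and arm. The share leaving PP is 1 − (1 − r)², which is 2.0%, 9.8% and 19.0% for r = 1%, 5% and 10%. Net change is fail-to-pass minus pass-to-fail, in percentage points.

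| True failure rate | r | Pass to fail | Fail to pass | Net change in chance of a PP pass |
|---|---|---|---|---|
| 1% | 1% | 0.16 | 0.36 | +0.20 |
| 1% | 5% | 1.50 | 1.46 | −0.04 |
| 1% | 10% | 7.08 | 1.39 | −5.69 |
| 2% | 1% | 1.02 | 0.81 | −0.21 |
| 2% | 5% | 6.05 | 2.90 | −3.15 |
| 2% | 10% | 10.92 | 3.22 | −7.70 |

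With all 111 subjects the chance of passing is about 92% at a 1% failure rate and 77% at 2%. Low restart rates have almost no net effect; higher ones cost power.

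**Step 6. False passes.** With true failure rates of 7% versus 2%, which is exactly at the margin, the PP pass rate stays at 4.6% for r = 0, 5% and 10%. At 6% versus 1% it moves from 5.5% to about 6%.

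**The case against.** **PP serves more than the 30-minute endpoint.** The SAP also uses PP for secondary efficacy and time-to-event analyses, and symptoms are followed to 180 minutes. Insulin can compromise those data, so a strict PP set has some rationale. But the censoring rule already handles data after intervention, and it remains. It names only glucose and neuroglycopenic symptoms, a gap better closed by wording than by removing whole subjects.

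**The 30–90 minute window is disputed.** This stands. The synopsis and step 8a disagree, so not every restart before 180 minutes can be called compliant.

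**The numbers rest on assumed restart rates.** This also stands. Any random loss of subjects produces some changed verdicts, and most of what Step 5 shows is lost precision.

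**A reader might infer bias in favour of G-Pen**, because the exclusion follows the outcome and the decision is made by staff who know the treatment (SAP 4.4). The documents do not support this. Nothing shows that restarts would differ by arm, and the rule is fixed in advance. Step 8 names rising glucose as the trigger, so those removed would mostly be responders. If only successful visits lead to a restart, fail-to-pass changes at r = 10% and 1% failure fall from 1.4% to 0.7%, so the test becomes harder to pass. ITT and mITT keep these subjects with their observed 30-minute result, so any divergence would be visible.

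**Conclusion.** The conflict is real and should be corrected. For insulin at 90–180 minutes the SAP penalizes what the protocol permits. For any insulin after 30 minutes the exclusion does nothing for the primary endpoint and discards valid outcomes from the PP analysis.

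The main expected effect is a smaller PP set, lower precision and a harder PP test. Its size cannot be stated from the documents. Under the assumptions in the working, the chance of a PP pass hardly changes when 1% of visits have a restart, and falls by about 6 to 8 percentage points at 10%. The point does not show bias by arm, a materially easier false claim of non-inferiority, or any effect on ITT or mITT. Nor does it follow that the rule empties PP, because SAP 4.1 supports the limit of 180 minutes.

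**What to change.** Before database lock, replace the last sentence of the insulin bullet in SAP 5.3.6.2.1 with:

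> *Insulin started within 30 minutes after study drug injection is a major protocol deviation. Insulin started more than 30 minutes after injection is not a reason for exclusion from the PP population and leads only to censoring of subsequent glucose values and symptom assessments.*

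A fixed 30-minute limit settles PP membership for 30–90 minutes without first resolving the protocol's two statements on that window. Align the censoring text in SAP 4.1 so that it covers all symptom assessments.

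An entry in SAP section 10 is needed only if a difference from the PP definition in Protocol 13.3 remains. One does remain for as long as SAP 5.1.3 keeps its clause on major deviations.

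The cost is one replaced sentence, a matching edit in 4.1 and, if needed, one line in section 10. The protocol, the data collected and the study procedures are unchanged, so the IRB/IEC review of protocol modifications in Protocol 17.1 is not triggered.
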